1.5 Study Rationale

Building upon our initial preliminary study and drawing from our institutional experience in online adaptation, as well as our capability to acquire high-quality CT scans while the patient is on the treatment table, the focus of this study is to demonstrate the feasibility of implementing this workflow for clinical use.

By using an online adaptation approach, we will combine the advantages of proton dosimetry while addressing the dosimetric challenges posed by proton therapy due to daily anatomical and tissue density variations. Establishing this workflow has the potential to enhance the effectiveness of proton therapy while simultaneously minimizing the adverse effects and radiation-related toxicity.

This study's objective is to demonstrate clinical feasibility and safety of the Proton Adaptive RadioTherapy (PARTy) workflow for patients who are suitable candidates for proton therapy and who could benefit from online adaptation based on anatomical considerations. We aim to demonstrate successful completion of the PARTy workflow in at least 70% of adaptive treatment fractions throughout the treatment delivery process.

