2.0 OBJECTIVES AND ENDPOINTS

Objectives	Endpoints
Primary	
To assess the feasibility of online proton adaptive radiotherapy based on successful delivery of more than 70% of attempted fractions where treatment adaptation is indicated.	
Successful completion of online adaptive proton radiotherapy workflow through treatment delivery in at least 70% of planned adaptive fractions.
 
Success will be defined as PARTy plan creation and delivery of the fraction using the study workflow in one on-table attempt. Unsuccessful planning and workflow delivery will be defined as multiple attempts of the PARTy workflow for one treatment fraction without treatment delivery such that the study workflow is abandoned.

Secondary	
1. To assess the safety of online proton adaptive radiotherapy.	1. Grade 2+ radiation-related toxicity at 3 months as measured by CTCAE v5.0.
Exploratory	

 To assess patient tolerability and satisfaction with online proton adaptive radiotherapy process. To assess dosimetric differences for target coverage and organ at risk (OAR) sparing between adaptive and non-adaptive proton therapy. 	
 Patient reported experience measures (PREMs). Dosimetry evaluation and comparison to non-adapted pre-plan.

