5.0 TREATMENT PLAN

The treatment will consist of stereotactic body radiation therapy, administered as 5 fractions. All patients will undergo standard initial consultation, pre-treatment simulation, and planning in accordance with institutional standards. When patients present for each treatment, the initial pre-plan will be generated and assessed for safety and coverage of the treatment area. In addition to this, a new adapted plan will be generated. Both plans will then be compared, and the plan deemed to be most appropriate will be carried out. This process will occur for each treatment.

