5.1.6 Adaptive Treatment Planning

When patients present for each proton treatment session, the initial treatment pre-plan will be generated based on the anatomy of the day. In addition to this, a new adapted treatment plan will be generated and re-optimization will be performed for dose adaptation to allow for acceptable sparing of normal structures (i.e., not violating the predetermined hard constraints based on safety constraints that are

already approved of for routine, clinical use). Dose adaptation can also be done in cases where on the volumetric imaging attained, there is noted to be violation of previously met hard constraints.

The supervising physician will review the adapted plan and prior non-adapted scheduled plan. Comparison will be made with initial pre-plan assessing for meeting OAR constraints and/or improvement of target coverage. The decision to proceed with the adaptive radiation is under the treating physician's clinical discretion where they feel tumor coverage may be impacted by interfraction motion of patient's anatomy and adaptive treatment may improve coverage based on pre-specified criteria (typically improvement in radiation dose coverage of the tumor or reduction of excess dose to a nearby organ which would increase toxicity). Subsequently, decision will be made if treatment will proceed with adapted plan or with initial pre-plan.

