5.2 Definitions of Evaluability

Endpoint	In order to be evaluable for this endpoint, a patient must...
Primary: feasibility of online proton adaptive radiotherapy	Have received at least one fraction of SBRT.
Secondary: G2+ toxicity at 3 months	
Exploratory: dosimetry evaluation and comparison to non-adaptive workflow	
Exploratory: PREMs	Have received at least one fraction of SBRT and completed PREMs.

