11.0 STATISTICAL CONSIDERATIONS

11.1 Definition of Primary Endpoint

Feasibility: Feasibility will be defined as successful completion of online adaptive proton radiotherapy workflow through treatment delivery in at least 70% of planned adaptive fractions..

Success will be defined as PARTy plan creation and delivery of the fraction using the study workflow in one on-table attempt. Unsuccessful planning and workflow delivery will be defined as multiple attempts of the PARTy workflow for one treatment fraction without treatment delivery such that the study workflow is abandoned.

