11.4 Statistical Analysis Plan

The primary objective is to demonstrate that online proton adaptive radiotherapy is feasible by confirming that adaptive treatment can be delivered in more than 70% of treatment fractions where treatment adaptation is indicated.

Our principal objectives in this trial will be to determine the feasibility for online proton adaptive radiotherapy. If we can successfully deliver treatments for more than 70% of treatment fractions where treatment adaptation is indicated while maintaining the safety, then we will consider this study as having provided sufficient pilot data to support more widespread study of online proton adaptive radiotherapy. Historical controls reference 70% as the definition of feasibility, so we have utilized that for our primary endpoint. Basic descriptive statistics will be used to evaluate feasibility. The long-term goals will be to improve patient outcomes and care by improving target coverage and decreasing radiation toxicity.

Regarding toxicity, we will report descriptive statistics for acute toxicity at a three-month time point. Toxicity rates are anticipated to be identical or improved to those of other linear accelerator based SBRT treatments. Other than the online adaptation component of the treatment plan, patients will receive disease site specific standard-of-care dose and fractionation treatment plan. Therefore, further prospective toxicity assessments are not indicated. Given that no prior data exists for online adaptive proton radiotherapy, we will report descriptive statistics. Descriptive statistics will be calculated on all variables. Frequencies will be computed for all binary/categorical variables, and continuous variables will be summarized using medians, quartiles, and ranges. Patient satisfaction measured with PREMS will be evaluated using descriptive statistics. As a pilot study we will establish these baseline parameters.

For the dosimetry exploratory endpoints, non-parametric equivalents (Wilcoxon test) will be conducted to compare plan quality between simulated pre-plans and online adaptive plans. Further analysis may be conducted with ANCOVA to estimate how the baseline covariates associated simulated pre-plans and online adaptive plans. The ANCOVA will be presented with least square (LS) mean estimate. Two-sided 95% confidence intervals for the mean changes and p-values will also be reported.

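### The primary feasibility rule has conflicting, undefined denominators, two inequalities and unclassified fraction outcomes, so the same data can pass or fail the 70% mark

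*Combined protocol and SAP*

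**What the plan says.** The protocol and SAP state the 70% rule in four ways, all in current text:

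- **Objective** (synopsis, section 2.0, repeated in Appendix D): "successful delivery of more than 70% of attempted fractions where treatment adaptation is indicated".
- **Endpoint** (synopsis, section 2.0, section 11.1): workflow completed "through treatment delivery in at least 70% of planned adaptive fractions".
- **Rationale** (section 1.5): "successful completion of the PARTy workflow in at least 70% of adaptive treatment fractions".
- **Analysis plan** (section 11.4): "adaptive treatment can be delivered in more than 70% of treatment fractions where treatment adaptation is indicated".

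Section 11.1 defines a successful fraction as "PARTy plan creation and delivery of the fraction using the study workflow in one on-table attempt". It defines an unsuccessful one as several attempts at the same fraction with no delivery and the workflow given up.

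Under sections 5.0 and 5.1.6, each session produces both the pre-plan on the day's anatomy and a new adapted plan. Section 5.0 continues: "Both plans will then be compared, and the plan deemed to be most appropriate will be carried out". Section 5.1.6 has the physician review both plans and then says: "Subsequently, decision will be made if treatment will proceed with adapted plan or with initial pre-plan". The decision to adapt is left to clinical discretion. The criteria are called pre-specified but are described only by what they typically are.

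For the primary endpoint, section 5.2 requires a patient to "Have received at least one fraction of SBRT". Appendix D has a yes/no column for whether the patient was feasible, which is defined nowhere.

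**The concern.** In this design the denominators are different quantities. An adapted plan is generated at every session, so attempted fractions come close to all fractions. Fractions where adaptation is indicated can be far fewer, because the physician may choose the pre-plan. No section defines *attempted*, *indicated* or *planned adaptive* for counting, or says which version governs.

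No time is fixed for recording that adaptation is indicated. If an adapted plan turns out inadequate or late and the pre-plan is delivered, the fraction could be logged as not indicated and so leave the denominator. The failure definition does not prevent this, because a single failed attempt followed by the pre-plan is not the multi-attempt abandonment it describes.

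Section 11.4 plans only descriptive statistics for feasibility. It makes passing 70%, with safety maintained, the condition for regarding the pilot as support for wider study. The point estimate is thus the whole feasibility half of that decision, and its definition carries all the weight.

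**Working it through.** **Inputs.** 10 evaluable patients (section 11.3) and 5 fractions each (section 5.1.1) give at most 10 × 5 = 50 fractions. The threshold is 70%. The plan states no alpha, power or required number of successes, so there is no figure of its own to reproduce. The splits and removal rates below are assumptions.

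**1. Same data, different denominators.** Suppose 50 scheduled fractions split as follows: 31 delivered adapted in one attempt, 3 on a second attempt, 6 abandoned, 8 treated with the pre-plan after review, 2 not attempted.

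| Denominator | Rate | Against 70% |
|---|---|---|
| Planned, read as all scheduled | 31/50 = 62.0% | fail |
| Attempted | 31/(50 − 2) = 31/48 = 64.6% | fail |
| Attempted and indicated, with pre-plan fractions taken as not indicated | 31/(48 − 8) = 31/40 = 77.5% | pass |

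The 3 second-attempt deliveries are unclassified by section 11.1. In the last row they count as non-successes. Dropping them instead gives 31/37 = 83.8%.

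**2. Non-successes leaving the denominator.** Take 30 successes and 20 non-successes in 50 fractions: 30/50 = 60%, a fail. If *r* non-successes are recorded as not indicated, the rate is 30/(50 − *r*).

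- *r* = 7: 30/43 = 69.8%, fail.
- *r* = 8: 30/42 = 71.4%, pass under either inequality.

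**3. Chance of passing.** Let *p* be the true one-attempt success rate and *q* the chance that a non-success leaves the denominator. With independent fractions,

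P(pass) = Σₛ Σᵣ Bin(s; 50, p) × Bin(r; 50 − s, q) × 1[s/(50 − r) > 0.70].

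At *p* = 0.60:

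| *q* (assumed) | P(rate > 70%) |
|---|---|
| 0 | 5.4% |
| 10% | 13.9% |
| 25% | 32.3% |
| 50% | 76.3% |

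**4. The two inequalities.** With 50 fractions, *at least 70%* needs 35 successes and *more than 70%* needs 36. They disagree only at exactly 35/50, which has probability 12.2% at a true rate of 70%, about 9% at 65% or 75%, and 3% at 80%. Exactly 70% is possible only when the denominator is a multiple of 10. With 45 fractions, both versions need 32.

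**5. Outcomes against section 11.1.**

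| Outcome | Success? | Failure? |
|---|---|---|
| Adapted, delivered in one attempt | yes | no |
| Several attempts, none delivered, abandoned | no | yes |
| Adapted, delivered on a second attempt | no | no |
| One failed attempt, then the pre-plan | no | no |

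**The case against.** The strongest reply is that a reader might infer more than the documents say.

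- **Timing of the indication.** One might read section 5.1.6 as saying that *indicated* is decided only after the adapted plan has been seen. It does not. It times the choice of which plan to deliver. The synopsis describes evaluation for replanning against prespecified dosimetric objectives, and section 5.1.6 also allows adaptation where the day's imaging shows hard constraints violated, which could be seen beforehand. This stands. What remains is that no definition or recording time exists, so classification after the result is possible.
- **Bias.** One might conclude that the indicated version is biased upward. Leaving out fractions where the pre-plan was truly adequate is a different target quantity, not bias. Bias needs a workflow failure relabelled as not indicated, and a multi-attempt abandonment is expressly a failure. This also stands.
- **Evaluability.** One might infer that patients whose attempts all fail drop out and are replaced. Enrolled patients must be suitable for non-adaptive proton SBRT (section 1.7.1), and the pre-plan is assessed at every session, so such a patient would ordinarily still receive a fraction. Replacement is only implied by the target of 10 evaluable patients.
- **Scale.** This is a small descriptive pilot with no test, and its go decision also depends on safety. That limits the consequence but does not settle which rate is to be compared with 70%.

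**Conclusion.** The point holds and should be corrected before the feasibility data are examined. The current text gives conflicting, undefined denominators and an incomplete classification of fractions, and with these the same data can fall on either side of 70%. In the illustration, relabelling 8 of 20 non-successes is enough to turn 60% into a pass. At a true rate of 60%, the chance of passing rises from 5.4% to between 13.9% and 76.3% over the assumed removal range of 10% to 50%.

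These sizes assume that all 50 fractions are attempted, that *planned* means all scheduled, and that fractions are independent. Five fractions within a patient are likely to be correlated, so the probabilities are illustrative only. The removal rates are not estimates of what investigators will do, and the documents do not show that any failure will be relabelled. The inequality conflict is minor, and the evaluability wording is a secondary point.

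**What to change.** Use one sentence in the synopsis, sections 1.5, 2.0, 11.1 and 11.4, and Appendix D, with one inequality and one denominator.

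1. **Denominator.** Fractions recorded as indicated for adaptation, using the patient's prespecified dosimetric criteria applied to the pre-plan on that day's CT. Make the record before the adapted plan is reviewed. It is for counting only and does not affect the physician's choice of plan to deliver.
2. **Classification.** Only adapted delivery in one on-table attempt is a success. Every other fraction in the denominator, including second-attempt delivery and reversion to the pre-plan, is a non-success reported by reason.
3. **Required sensitivity analysis.** The success rate over all fractions at which the workflow was started.
4. **Appendix D.** Define or remove the per-patient feasible yes/no column.
5. **Secondary.** Count a patient as evaluable for the primary endpoint once the adaptive workflow has been started for at least one fraction.

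The cost is a wording amendment and one record per fraction. Each patient's criteria must also be on file before treatment, because section 5.1.6 describes them only in general terms and section 5.1.8 sets constraints case by case. The reported rate may be less favourable. Another clearly stated denominator with full accounting of fractions would also remove the contradiction. Recording the indication first has the added merit of keeping the denominator independent of the workflow result.

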3.0 STUDY POPULATION

3.1 Inclusion Criteria

Patients must meet all of the below criteria in order to be enrolled to this study.

1. Oligometastatic or primary malignancy planned for proton SBRT. Disease site should be biopsy-proven primary disease of solid tumor histology with the exception of Hepatocellular carcinoma (HCC). HCC does not need to be biopsy proven if imaging and clinical findings are consistent with the diagnosis.

2. Must be deemed medically fit for proton SBRT by the treating physician.
3. Prior radiation therapy is allowed.
4. At least 18 years of age.
5. Karnofsky \geq 70% (see Appendix A).
6. Because radiation therapy is known to be teratogenic, women of childbearing potential and men must agree to use adequate contraception (hormonal or barrier method of birth control, abstinence) prior to study entry and for the duration of study participation. Should a woman become pregnant or suspect she is pregnant while participating in this study, or a male suspect he has fathered a child, s/he must inform the treating physician immediately.
7. Ability to understand and willingness to sign an IRB approved written informed consent document.

3.2 Exclusion Criteria

Patients must not meet any of the criteria below in order to enroll to the study.

1. Histology of small cell carcinoma. Mixed histologies with a predominantly small cell component are also exclusionary.
2. Patients with a prior or concurrent malignancy whose natural history or treatment does not have the potential to interfere with the safety or efficacy assessment of the investigational regimen are eligible for this trial.
3. Medical contraindication to proton therapy or any other condition that in the opinion of the treating radiation oncologist, renders the patient unfit for SBRT
4. Uncontrolled intercurrent illness including, but not limited to, ongoing or active infection, symptomatic congestive heart failure, unstable angina pectoris, or cardiac arrhythmia.
5. Pregnant and/or breastfeeding. Women of childbearing potential must have a negative serum or urine pregnancy test within 14 days of study entry.

3.3 Inclusion of Women and Minorities

Both men and women and members of all races and ethnic groups are eligible for this trial.

4.0 REGISTRATION AND ENROLLMENT PROCEDURES

The following steps must be taken before enrolling patients on this study:

1. Registration of patient in the Siteman Cancer Center database
2. Assignment of unique patient number (UPN)
3. Confirmation of patient eligibility

Patients must not start any protocol intervention or procedures prior to signing of informed consent.

4.1 Registration in OnCore Database

Patient registration to the Siteman Cancer Center OnCore database must occur within one business day of the patient signing consent.

4.2 Assignment of UPN

Each patient will be identified with a unique patient number (UPN) for this study. The UPN must not include patient initials or other identifying information. All data will be recorded with this identification number on the appropriate CRFs.

4.3 Confirmation of Patient Eligibility and Enrollment

Patient eligibility will be confirmed using the information listed below

1. Completed eligibility checklist, signed and dated by a member of the study team
2. Copy of appropriate source documentation confirming patient eligibility

4.4 OnCore Subject Status Definitions

Note: subject status should not be updated in OnCore until the subject is actively in that status; future dates are not allowed.

Subject Status	Definition
Consented	Patient has signed an IRB approved consent for the trial.
Eligible	Patient eligibility has been confirmed by Washington University PI or delegate.
Not Eligible	Patient did not meet eligibility criteria for the trial. Note that if a patient is determined to be eligible but never initiates study participation, they are not considered a screen fail.
On Study	Patient is confirmed eligible for the study and enrolled.
On Treatment	Patient is receiving study therapy. On Treatment date should be the date of the first study treatment.

Off Treatment	Patient has discontinued study therapy. Off Treatment date should be the last day any study treatment was administered.
On Follow Up	On Follow Up date is the same as the Off Treatment date
Off Study	Patient has fully discontinued all study procedures (including any follow-up procedures and/or review of medical record for outcomes data).

4.5 Screen Failures

Screen failures are defined as participants who consent to participate in the clinical trial but are not subsequently randomized to the study intervention or entered in the study. A minimal set of screen failure information is required to ensure transparent reporting of screen failure participants, to meet the Consolidated Standards of Reporting Trials (CONSORT) publishing requirements and to respond to queries from regulatory authorities. Minimal information includes demography, screen failure details, eligibility criteria, and any serious adverse event (if applicable).

4.6 Strategies for Recruitment and Retention

Patients will be accrued on basis of presentation to the radiation oncology clinic amenable to proton SBRT. Potential participants will be identified in the inpatient and outpatient radiation oncology clinic setting, as well as from the multidisciplinary spine tumor board. Patients will be approached regarding participation at or around the time of their radiation oncology consultation visit. Patients will be treated at a single facility, at the S. Lee Kling Proton Therapy Center, as the technology required for this study is confined to this center. We anticipate an accrual rate of approximately 10 patients per year, or an estimated study accrual period of 8-12 months. There will be no compensation or incentives offered for study participation.

5.0 TREATMENT PLAN

The treatment will consist of stereotactic body radiation therapy, administered as 5 fractions. All patients will undergo standard initial consultation, pre-treatment simulation, and planning in accordance with institutional standards. When patients present for each treatment, the initial pre-plan will be generated and assessed for safety and coverage of the treatment area. In addition to this, a new adapted plan will be generated. Both plans will then be compared, and the plan deemed to be most appropriate will be carried out. This process will occur for each treatment.

5.1 Radiation Therapy Guidelines

5.1.1 Dose and Fractionation

Radiotherapy will consist of stereotactic body therapy, to be given over five fraction course, delivered once daily or once every other day for a period of one to two weeks, for a total of five treatments. Patients will be planned for an initial

prescription dose at the discretion of the treating physician, delivered in five total fractions to the PTV, with dose adaptation based on safety constraints that are already approved of to prevent OAR injury.

